We select a common number of clusters within each of the four study countries. The goal is to have enough clusters so that the study is powered to detect a 0.15 control group standard deviation effect (Glass’s Delta) on the Vaccine Trust Indicator (VTI), equivalent to a 7ppt. effect on the vaccination rate outcome, with 80% power and 95% confidence in an analysis that pools that data from the four countries. For the power analysis for the VTI (our primary outcome variable), we assume the control group VTI outcomes are normally distributed (we use this assumption due to the unavailability of actual distributional information on the VTI for the countries under investigation at the time of power calculation) and that all outcomes are normalized relative to the control group standard deviation. For vaccination rates, we used the most recently available (as of summer 2023) health-district-level COVID-19 vaccination rates (when available) as the input data. We simulated a 0.15 control group SD effect, which was equivalent to a 7 ppt. effect on vaccination, and then evaluated what sample size would be needed to achieve 80% power with 95% confidence. The power analysis showed that having **16 treated clusters and 16 control clusters per country and 24 households per cluster** would suffice. This implies $(16+16)*24 = 768$ **households sampled per country**, with an **overall sample size of 3,072 households and 128 clusters** across all four countries.

The study aims to increase vaccine trust, with COVID-19 vaccination being the primary basis for assessing current hesitancy. In each country, our primary focus lies on the two largest, most densely populated cities. This strategic decision is driven by the critical need for vaccination in these regions, owing to their heightened potential for disease transmission and the prevailing low COVID-19

vaccination rates. In each priority locality, clusters are defined as neighbourhoods served by health centers or clinics that meet the following criteria:

- The health center must offer COVID-19 vaccination services and services for other target vaccines (varies by country).
- For each targeted city, the health facilities used for defining the clusters must be separated by a distance of at least 4 to 5 km. This precautionary measure is taken to prevent potential spillover effects.

We proceed by describing the criteria employed for selecting priority districts within each country.

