In Cote d’Ivoire and Senegal, the Health Ambassadors are selected from recently graduated students from graduate programs in medicine, nursing, biomedical, health sciences, or public health. In Malawi and Zimbabwe, the Health Ambassadors are selected from existing community health volunteers and community health nurses. To the extent possible, we will prioritize Community Health Workers who have completed post-graduate education in health. This selection is motivated by evidence from the country contexts of this research showing that populations trust those with relevant expertise (e.g., doctors, nurses, or health workers) more than other types of leaders when discussing health issues. In Malawi, for example, while about half of those not planning to vaccinate against COVID-19 are likely to trust COVID-19 vaccine information when health professionals give it, only 10% and 7% claim to trust COVID-19 vaccine information when it comes from religious or community leaders, respectively.

Given cultural norms in the context of the countries in which we work and to promote the compliance of local populations to work in synergy with the Health Ambassador, we aim to recruit Health Ambassadors that come from the regions in which they would be operating in the context of the study.

Recruitment Process

In Cote d’Ivoire and Senegal we employ a recruitment process in partnership with medical or health sciences faculties and schools to identify potential health ambassadors. This process allow recently graduated students from these institutions, who are seeking opportunities and are available during the intervention period, to express their interest in becoming health ambassadors for this intervention. Preference are given to graduates in medical, nursing, biomedical, or related fields. To accomplish this, the project research team in each country (Côte d’Ivoire and Senegal) establish contact with multiple medical or medical science faculties to acquire the contact details of recent graduates in the relevant medical disciplines.

In Malawi and Zimbabwe, we work with the health authorities in the relevant cities to identify community health volunteers and nurses who meet the qualifications listed above.

For all candidate Health Ambassadors, we convey information on duties, locations, and time commitments. We collect information pertaining to the qualification criteria:

- Assessment of willingness to work on a volunteer basis, intrinsic motivation, and empathy;

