7. Role playing exercises and written examinations to ensure preparedness.

Trainees are scored based on the role-playing exercises and written examination.

Monitoring of the Health Ambassadors

Weekly check-in meetings: The research team will conduct weekly check in sessions lasting 1 to 2 hours with the Health Ambassadors. These sessions will allow the team to assess the progress of the Health Ambassadors' work and address any challenges they may be encountering. During these meetings, the Ambassadors will have the opportunity to seek guidance and discuss any difficulties they are facing.

WhatsApp groups: Once the intervention commences, a dedicated WhatsApp group will be established for each country to serve as an official communication platform between the Health Ambassadors and the research team.

Outcome Measurement

Outcomes will be measured through endline surveys that will be timed so as to occur in the month following the week period of engagement in each community. We propose to measure the impact of the intervention in terms of both vaccine trust, other attitudinal outcome measures and behavioral outcome, with a standardized measurement strategy for households in treated and control clusters. We also plan to obtain process-relevant indicators from the Health Ambassadors as well as contextual information from staff at the focal health facilities.

Household Survey

The full household survey appears as an accompanying document. (The household questionnaire can be accessed [here](#).) In the sections below, we describe the key sections and key questions.

Household Survey Data Structure

The data will be structured as (1) a household roster for all households' members including adults and children residing in the household and (ii) an individual questionnaire administered to the head of household or (if the head is unavailable) an adult who is accepted by the household members as speaking on behalf of the household.

Manipulation Check Measure

First, in the individual questionnaire, we will ask questions to assess the extent to which the Health Ambassadors' visits represented any meaningful increase in receipt of information about vaccination:

- Have you received any information about vaccination in the past three months?

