- From whom did you receive it? (Do not read responses; add checklist: Health Ambassador, doctor, nurse, health worker, religious leader, chief or traditional leader, other relative or household member, internet/social media, books, other: specify).

[Note for Enumerator: For the control group, if the information was obtained from a friend, acquaintance, or relative who is not a family member, please provide the following details regarding the source of the information:

- A. Name of the person:
- B. Place of residence:
- C. Content of the message received regarding vaccines:

- What types of vaccinations were featured in these vaccination awareness campaigns? COVID-19, HPV, Measles, etc. [Enumerators: This is a Multiple-Choice question; kindly let the household member respond.]
- For each of the vaccine information campaigns you attended, could you please share the outreach strategy used by the organizations responsible for the campaign to make you aware of this specific type of vaccine? Billboards, Posters, Radio announcements, Door to door, Public announcements at public events, etc.
- What is the core message of each of these vaccine awareness campaigns?

Primary outcome measure

Vaccine Trust Indicator

Our primary outcome is the perceived change in vaccine confidence/receptivity following health ambassador discussions with households on vaccination trust (VTI).

The main focus is on COVID-19 or other targeted vaccine confidence, evaluated through the Vaccine Trust Index (VTI). The VTI measures confidence in the importance, safety, and efficacy of vaccines, with each item rated on a 10-point scale ranging from 1 ('strongly disagree') to 10 ('strongly agree'). We will use the 6-item VTI to assess the effectiveness of our Health Ambassador (HA) intervention, designed to enhance dialogue among adults who are vaccine-hesitant and improve trust and confidence in vaccines. The VTI, a validated tool ([Ellingson et al., 2023](#)) used in various contexts (

[Ellingson et al., 2023](#)), genuinely aids us in observing changes in trust and the shift from hesitancy to confidence. Below are the different questions to capture the Vaccine Trust Indicator.

Please give your level of agreement with each statement using the scales provided (where 1 = strongly disagree/strongly against vaccination and 10 = strongly agree/strongly in favor of vaccination).

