- 7.2. Which of the following statements best describes your status regarding the [XXX] vaccine? (I am fully vaccinated; I am not vaccinated, but if someone brought it to me I would take it; I am not vaccinated, and I do not want to be vaccinated)
 - 7.2.1. [XXX] = ask for all target vaccinations in the country
- 7.3. Suppose that COVID cases started to rise again. If the health ministry recommended that you get vaccinated or boosted for COVID, would you get it? (Definitely not, Probably not, maybe/maybe not, probably yes, definitely yes).
- 7.4.
8. Trust in healthcare system:
 - 8.1. In the past 3 months how often have you visited a nurse, doctor, or community health worker for any health? (Yes/No)
 - 8.2. In the past 3 months how often have you visited a nurse, doctor, or community health worker for vaccination related issues? (Yes/No)
 - 8.3. In the past 3 months how often have you visited a nurse, doctor, or community health worker for vaccination related issues? (Never, only sometimes. often, always)
 - 8.4. In general, how often have you visited a nurse, doctor, or community health worker for any health-related issues? (Never, only sometimes. often, always)
 - 8.5. In general, how often have you visited a traditional medicine practitioner or a traditional healer for any health-related issues? (Never, only sometimes. often, always)
 - 8.6. Which of the following statements is closest to your view? Choose Statement 1 or Statement 2.

Statement 1: Whenever I experience a health problem, I tend to seek medical advice from professionals in modern medicine.

Statement 2: Whenever I face a health issue, my preference is to consult traditional medicine practitioners for guidance and treatment.

Agree with neither [Do not read]
 - 8.7. How confident are you in the government's healthcare system to help prevent you and your loved ones from getting very sick from diseases? (Not at all; a very little bit; somewhat; mostly confidence; totally confident)
 - 8.8. If you wanted to verify the safety of a medication or vaccination, what is the best source to do so? (Do not read responses: Health Ambassador, doctor, nurse, health

worker, religious leader, chief or traditional leader, other relative or household member, internet/social media, books, other: specify).

- 8.9. I would like to offer you an opportunity to sign up to receive Ministry of Health bulletins via text [ASSUMING SUCH A SERVICE EXISTS]. Would you like me to sign you up for this service? (Yes/No)

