- For the global index, we will use the standard asymptotic p value and a two-sided null hypothesis with 95% confidence.
- If the global p-value rejects the null, then for the grouping-specific indices, we will use a Benjamini-Hochberg FDR correction for the 4 p-values.
- For any grouping index that rejects the null, we will use the Benjamini-Hochberg FDR correction for the item level p-values.

For estimating peer effects, we will use the same specification (2), with l indexing the peer respondent and $Treated_i$ indicating the treatment status of the person that recommended them.

For our behavioral outcome measured in the household roster, we will estimate the average treatment effect on the pooled vaccination rate using the following regression specification:

$$y_{vji} = \alpha + \beta Treated_i + Vaccine FE_v + Rand. Block FE_{b[i]} + X_{ji}'\gamma + \epsilon_{vji} , \quad (2)$$

where v indexes the vaccine, j indexes the individual adult in the household roster, i indexes the household, and $b[i]$ indexes the randomization block for household i . The variable $Treated_i$ is an indicator for whether the household is in a treated cluster or not. Then, $Vaccine FE_v$ are fixed effects (dummy variables) for the different vaccines and $Rand. Block FE_{b[i]}$ are fixed effects (dummy variables) for the randomization blocks. The covariate vector X_{ji} includes the following elements:

- Indicator for female of individual j ,
- Age for individual j ,
- Level of education for individual j ,
- Pre-intervention vaccination rate in the household's cluster.

We calculate cluster-robust standard errors taking the error term ϵ_{vji} to be clustered at the level of the randomization cluster. We hypothesize that $\beta > 0$, and we test using a two-sided test (allowing for the possibility that effects could go in the opposite direction as what is hypothesized) with 95% confidence. If we reject the null, we will then test effect on each individual vaccine, using the Benjamini-Hochberg FDR correction for the vaccine-level p-values.

Effect Heterogeneity with Household Data

We propose an exploratory analysis of background conditions that may moderate the size of the treatment effects on behavior and attitudes. These include:

Respondent attributes:

- Gender,
- Age,
- Level of education,
- Ethnic group (coded for collectivist norms),
- Proximity to health center.

Health ambassador attributes:

- Gender,
- Age,
- Type of degree program,

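### Exposure questions and a control-only prompt precede the self-rated VTI, and recent health-worker contact, asked twice, sits under the trust heading

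*Protocol*

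**What the plan says.** **Order and prompts.** The Manipulation Check Measure section of the protocol opens: "First, in the individual questionnaire, we will ask questions to assess the extent to which the Health Ambassadors" visits added to the vaccination information that people received. The questions cover any such information in the past three months and where it came from. Health Ambassador is one code in a list that is not read out. An enumerator note then begins "For the control group, if the information was obtained from a friend, acquaintance, or relative who is not a family member", and asks for further details of that source. The VTI is described next: six self-ratings from 1 to 10, summed. Questions about the ambassador's visits go to treated households only and are listed after all outcomes (Household level process indicators). The Outcome Measurement section promises standardized measurement across the arms.

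**Trust items.** Under Secondary outcome measures, heading 8 (Trust in healthcare system), item 8.1 asks about visits in the past three months to a nurse, doctor or community health worker for any health matter. Item 8.2 reads "In the past 3 months how often have you visited a nurse, doctor, or community health worker for vaccination related issues? (Yes/No"). Item 8.3 has the same stem with answers from never to always. Item 8.8, on the best source for checking safety, has Health Ambassador as an unread code and no stated scoring.

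**Who the ambassadors are.** "In Malawi and Zimbabwe, the Health Ambassadors are selected from existing community health volunteers and community health nurses" (Recruitment and Mobilization of Health Ambassadors, Profile).

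**Use in the analysis.** The Analysis Plan sums standardized items into four groupings and the groupings into a global index. "For the global index, we will use the standard asymptotic p value and a two-sided null hypothesis with 95% confidence". Only if that test rejects are the groupings tested, and then the items.

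**The concern.** There are two separate routes by which exposure, rather than attitude, could produce a difference between the arms.

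The first concerns the primary outcome. An enumerator who must apply a control-only note has to know the arm at that point. The respondent has just been asked about vaccination information and its source. Self-ratings of trust follow. Agreeable answering or interviewer expectation could then differ by arm.

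The second concerns a secondary grouping. Contact with health workers is counted as trust, one question appears twice, and the visits that make up the intervention may be reported as such contact. A higher trust grouping could then show only that the visits took place. The same shift, diluted, would enter the global index that opens the hierarchy of attitude tests.

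**Working it through.** **Design figures.** (16 + 16) × 24 = 768 households per country; × 4 = 3,072, and 32 × 4 = 128 clusters. This matches the stated "overall sample size of 3,072 households and 128 clusters". The trial is to be "powered to detect a 0.15 control group standard deviation effect" on the VTI, "with 80% power and 95% confidence in an analysis that pools that data from the four countries". Without clustering, 2 × (1.960 + 0.842)² / 0.15² = 698 per arm, against 64 × 24 = 1,536. This allows a design effect of 2.20, so an ICC of (2.20 − 1)/23 = 0.052. No ICC is stated, so the power claim is consistent with about 0.05 but cannot be confirmed.

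**Route 1: order and arm awareness.** The protocol gives no input for the size of this bias. To show sensitivity only, take the ICC of 0.052. The SE is √(2 × 2.196/1,536) = 0.0535 SD. With an assumed bias b and no true effect, the two-sided 5% test rejects with probability Φ(b/SE − 1.96) + Φ(−b/SE − 1.96): 5% at b = 0, 16% at 0.05 SD and 46% at 0.10 SD.

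**Route 2: recall window.** Six weeks of engagement (Numbers and Timeline) plus up to 30/7 = 4.3 weeks to endline (Outcome Measurement) is 10.3 weeks, inside the 13 weeks that 8.1 to 8.3 cover. Each treated household is due at least two engagements in that time.

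**Route 2: size, with assumed inputs.**
- Nine items (8.1 to 8.9), equal weight, common inter-item correlation r. Items 8.2 and 8.3 are treated as perfectly correlated, and each moves by the same number of SDs, although 8.3 has four levels.
- Contact is 20% in control, and 40% or 50% in treated respondents in Malawi and Zimbabwe. There is no shift in Côte d'Ivoire or Senegal, and 8.1 is left unmoved.
- Item shift: (0.40 − 0.20)/√(0.2 × 0.8) = 0.50 SD, or 0.30/0.40 = 0.75 SD.
- Grouping shift: 2 × item shift / √(9 + 72r + 2(1 − r)). The root is 4.24, 5.00 and 5.66 at r = 0.1, 0.2 and 0.3.
- Share of households in the two countries (Table A1): (1,001 + 791)/3,773 = 0.475.
- Global index of four groupings with correlation g: pooled shift / √(4 + 12g), a divisor of 2.00 at g = 0 and 3.16 at g = 0.5.

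| Treated contact | r | Two countries | Pooled | Global, g = 0.5 to 0 |
|---|---|---|---|---|
| 40% | 0.1 | 0.24 | 0.11 | 0.04 to 0.06 |
| 40% | 0.2 | 0.20 | 0.10 | 0.03 to 0.05 |
| 40% | 0.3 | 0.18 | 0.08 | 0.03 to 0.04 |
| 50% | 0.1 | 0.35 | 0.17 | 0.05 to 0.08 |
| 50% | 0.2 | 0.30 | 0.14 | 0.05 to 0.07 |
| 50% | 0.3 | 0.27 | 0.13 | 0.04 to 0.06 |

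The result depends heavily on the assumptions. With control contact of 10 to 40%, and 10 to 50% of the remaining treated respondents counting the visit as contact, the shift where it occurs runs from 0.04 to 0.71 SD.

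**Dropping the duplicate only.** With eight items, one of them moved by 0.50 SD, the shift is 0.50/√(8 + 56r) = 0.14 to 0.10 SD for r = 0.1 to 0.3 in the two countries. Merging 8.2 and 8.3 reduces the leak but does not remove it.

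**The case against.** The questionnaire is a separate document that is not shown, so the exposure check may come first only in the description. A reader might also infer that ambassador contact itself is asked first. The text does not say so: the opening questions concern information and its source, the ambassador code is not read out, and the direct questions come after the outcomes.

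On the trust items, having visited a worker naturally means that the respondent went to the worker, whereas ambassadors come to the home. The source checklists code ambassadors separately from nurses and health workers. Control clusters keep their existing outreach. The four groupings are not named, so it is not fixed that all items under heading 8 are summed. Care-seeking can be read as revealed trust, and naming the ambassador unprompted in 8.8 may be an intended effect.

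Finally, treated households know that they were visited, and the treated-only questions reveal the arm in any order.

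Much of this limits the point without removing it. The stated order is the only one the protocol gives, and the control-only note departs from the promised standardization. The items do not say whether home visits count, and that ambiguity falls on one arm more than the other. The identical stems of 8.2 and 8.3 are plain in the text. Reordering cannot blind anyone, but it would protect the outcome answers from cues given earlier in the interview.

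**Conclusion.** The point holds as an inexpensive improvement to measurement. On the primary outcome, the stated order and the control-only prompt invite arm-dependent response or interviewer bias. Its direction is plausible and its size unknown; the rejection rates above rest on assumed biases and an ICC that the protocol does not state.

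On the trust grouping, the duplicated contact question and the overlap between ambassadors and the workers named can raise the score with no change in trust, if these items are summed and some respondents count the visits. The tabulated cases give 0.08 to 0.17 SD pooled for the grouping and 0.03 to 0.08 SD for a four-part global index. All of them rest on assumed contact rates.

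A reader might infer that this leak could by itself produce the 0.15 SD on which the trial is sized. The documents do not support that. The 0.15 SD is an effect on the VTI, which contains no contact item. The leak acts on a secondary grouping and, diluted, on the global gate. Nor do the documents establish that the visits are counted as contact at all.

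**What to change.** At endline:
- Ask the VTI and all attitude items before the exposure check and the ambassador process questions.
- Use the same source prompts in both arms.
- Keep only one of 8.2 and 8.3.
- Leave 8.1 to 8.3 out of the trust index and report them as service use, or add a clarifier that ambassador visits do not count.
- Score Health Ambassador in 8.8 the same as doctor, nurse or health worker.
- Name the four groupings and their items.

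The cost is a reordered form, a few changed words and a small loss of comparability with baseline wording and order. If the endline form is already fixed, the index exclusion, the scoring of 8.8 and the list of groupings can still be set in the analysis before the data are examined by arm. The question order would then remain as a stated limitation.

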The randomized controlled trial operate as a multisite locality-level cluster-randomized experiment across Côte d'Ivoire, Malawi, Senegal, and Zimbabwe. The treatment is whether a locality received "health ambassadors" in combination with any already-existing public outreach (treated = 1) versus no additional intervention above and beyond any already-existing public outreach (control = 0). We randomly assign half of the clusters to treatment and the other half to control. The randomization is stratified on the basis of city, and where possible, health district within city. The result will be a balanced block-cluster random assignment of 16 clusters to treatment and 16 clusters to control per country, for a total of 64 treated clusters and 64 control clusters. The statistical analysis will control for the block stratification.

Household Recruitment

Household Recruitment

We define households using the definition from the international Demographic and Health Surveys (eat from the same pot, live under the same roof, and share the same household head). In selected clusters, after obtaining approval from health district authorities to proceed with field activities, field enumeration staff (*separate from the health ambassadors*) will operate under the research team's supervision to employ the following process to identify the households to be surveyed in the cluster. As explained above, our target is 24 households per cluster. However, since the study is conducted in densely populated urban areas where households may migrate, field enumerators were instructed to survey 30 households per cluster to account for potential attrition. Due to logistical challenges, such as difficulties in finding eligible households during the survey period and data quality control measures that prompted some enumerators to survey more than 30 eligible households, cluster sizes ended up varying between 24 (in Zimbabwe) and 37 (in Côte d'Ivoire). Table A1 presents the total number of households and adults surveyed at baseline by country.

1. Using Google Maps, we map the outline of each cluster and geolocate the focal health facility where free vaccination is available for all of the target vaccines in the country.
2. We stratify the area into 5 or 6 bands of increasing distance from the health facility.
3. We randomly sample a geolocated point within each band.
4. Using Google Maps, we identify the home nearest to each of those sampled points.

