Please give your level of agreement with each statement using the scales provided (where 1 = strongly disagree/strongly against vaccination and 10 = strongly agree/strongly in favor of vaccination).

- 1.1. Thinking about vaccination in general, would you say you are...
1=strongly against vaccination, 10=strongly in favour of vaccination
- 1.2. I generally trust vaccine manufacturers or pharmaceutical companies
1=strongly disagree, 10=strongly agree
- 1.3. I generally trust the {country specific health department}
1=strongly disagree, 10=strongly agree
- 1.4. I understand how vaccination helps my body fight infectious disease
1=strongly disagree, 10=strongly agree
- 1.5. I feel it is important that I get vaccinated
1=strongly disagree, 10=strongly agree
- 1.6. Vaccination forms part of a healthy lifestyle
1=strongly disagree, 10=strongly agree

The items are summed to create a composite vaccine trust score. We will standardize in terms of control group standard deviations.

Secondary outcome measures

These secondary outcomes will be measured through a household questionnaire at baseline (before the intervention) and endline (after the intervention). The following questions will be asked to adult members of the household.

1. Vaccine uptake

- 1.1 For each vaccine and each target household members, the individual questionnaire will indicate whether the respondent (i) did not verbally affirm receiving the vaccination or provide documentation, (ii) verbally affirmed vaccination but did not provide documentation, or (iii) provided documentation of vaccination.

For respondents who have not been vaccinated due to time constraints or limited access to health centers, the survey will capture their intention to receive the vaccine if they were at a health center using the following question: Are you planning to be vaccinated for the [country specific disease] vaccine?

2. Knowledge about the disease: I will read you some statements and I would like you to tell me how much you agree or disagree with each statement. Please say whether you strongly agree, agree, neither agree nor disagree, disagree, or strongly disagree.
 - 2.1. [The targeted disease name] exists.
 - 2.2. I am aware of how [The targeted disease name] is transmitted.
3. To the best of my knowledge, [Targeted disease name from the list] require vaccines for their cure?
4. Vaccine/disease knowledge:

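### As written, the Ministry text-bulletin sign-up (item 8.9) is offered at baseline as well as endline, with no answer code for respondents who are already enrolled

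*Protocol*

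**What the plan says.** Four parts of the Protocol bear on this.

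- **Secondary outcome measures, opening sentences.** The timing rule covers the whole list: "These secondary outcomes will be measured through a household questionnaire at baseline (before the intervention) and endline (after the intervention". Next comes "The following questions will be asked to adult members of the household". Neither sentence exempts an item or restricts it to one arm.
- **Secondary outcome measures, heading 8 (Trust in healthcare system), item 8.9.** The respondent hears "I would like to offer you an opportunity to sign up to receive Ministry of Health bulletins via text", subject to a bracketed condition, "ASSUMING SUCH A SERVICE EXISTS". The recorded answer is to "Would you like me to sign you up for this service? (Yes/No". No code exists for someone who already receives the bulletins.
- **Outcome Measurement.** The general timing statement differs: "Outcomes will be measured through endline surveys that will be timed so as to occur in the month following" the engagement period. Measurement is to be the same in both arms, "with a standardized measurement strategy for households in treated and control clusters". The full questionnaire is a separate document and is not at hand.
- **Cluster Randomization.** Control is defined as "no additional intervention above and beyond any already-existing public outreach (control = 0".

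**The concern.** Most items in the list ask for an opinion, a belief or a recollection and can be repeated without harm. Item 8.9 cannot, because the first asking changes the respondent's status. Someone who accepts at baseline is enrolled, and at endline has nothing left to accept. That person may say Yes (already signed up, or happy to confirm), may say No (no need to sign up again), or may be skipped by the enumerator. The Yes/No field does not separate this No from a refusal.

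Two things are at stake. The first is the size of the between-arm difference on 8.9, the one item in its grouping that records an act in front of the enumerator. The second is that the study would itself have arranged some Ministry messaging before the intervention, which blurs the description of the control condition.

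**Working it through.** **Step 1: timing.** The opening of Secondary outcome measures is specific to this list and says baseline and endline. Outcome Measurement is general and names endline only. Under Household level process indicators, the Protocol assigns those questions to the endline survey explicitly, so it marks endline-only items when it means to. Item 8.9 has no such mark. The more specific text therefore puts 8.9 at both rounds, but the two statements do not agree and the questionnaire cannot be checked.

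**Step 2: effect of the coding on the difference.** The Protocol gives no acceptance figures, so these inputs are assumptions for illustration:

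- *b* = share enrolled at baseline, equal in expectation in both arms: 10%, 30% or 50%
- *s0* = 20% and *s1* = 27% = share accepting at endline among those not yet enrolled, control and treated
- planned respondents per arm = 64 clusters × 24 households = 1,536, as if the service existed in all four countries

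Formulas:

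- Already enrolled coded Yes: control level *b* + (1 − *b*)·*s0*; difference (1 − *b*)(*s1* − *s0*)
- Already enrolled coded No: control level (1 − *b*)·*s0*; difference (1 − *b*)(*s1* − *s0*)
- Already enrolled excluded: control level *s0*; difference *s1* − *s0*; number per arm 1,536(1 − *b*)

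The Analysis Plan standardizes outcomes by the control-group SD, so each difference is divided by √(p(1 − p)), where p is the control level.

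| *b* | Coding | Control level | Difference (points) | Control SD | Standardized | Number per arm |
|---|---|---|---|---|---|---|
| 10% | Yes | 28% | 6.3 | 0.449 | 0.140 | 1,536 |
| 10% | No | 18% | 6.3 | 0.384 | 0.164 | 1,536 |
| 10% | Excluded | 20% | 7.0 | 0.400 | 0.175 | 1,382 |
| 30% | Yes | 44% | 4.9 | 0.496 | 0.099 | 1,536 |
| 30% | No | 14% | 4.9 | 0.347 | 0.141 | 1,536 |
| 30% | Excluded | 20% | 7.0 | 0.400 | 0.175 | 1,075 |
| 50% | Yes | 60% | 3.5 | 0.490 | 0.071 | 1,536 |
| 50% | No | 10% | 3.5 | 0.300 | 0.117 | 1,536 |
| 50% | Excluded | 20% | 7.0 | 0.400 | 0.175 | 768 |

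Yes and No coding give the same raw difference, smaller than with exclusion by the factor 1 − *b*, and the sign never changes. The standardized size does depend on the code: at *b* = 50% it runs from 0.071 to 0.175, a ratio of about 2.5.

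**Step 3: what exclusion costs.** At *b* = 50%, ignoring clustering, the difference divided by its standard error is:

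- Excluded: 0.07 / √[(0.20·0.80 + 0.27·0.73)/768] = 3.2
- No: 0.035 / √[(0.10·0.90 + 0.135·0.865)/1,536] = 3.0
- Yes: 0.035 / √[(0.60·0.40 + 0.635·0.365)/1,536] = 2.0

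On these inputs, the loss of respondents does not make the comparison less sensitive.

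**The case against.** The strongest reply is that baseline delivery is not established. One blanket sentence covers a long list, Outcome Measurement speaks only of endline, and 8.9 still carries a drafting condition about whether the service exists. The questionnaire or an analysis plan not shown may already settle both timing and coding. This stands to the extent that the first action must be to confirm the timing. It does not remove the point, because the list's own timing statement is in the Protocol and includes 8.9.

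A reader might also infer more than the document supports:

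- **Contamination of the control arm.** A baseline offer would go to both arms before the intervention, so enrolment is balanced in expectation. It could dilute an effect but does not bias the randomized contrast. The offer is also conditional on an existing Ministry service, which sits close to the outreach that the control definition allows.
- **Vaccine outreach.** The item mentions Ministry of Health bulletins and does not describe their content.
- **An item that cannot be scored.** A filter question and a rule would settle it. That the most trusting respondents would count as the least trusting requires a No coding that the Protocol does not state.
- **Damage to the global index.** The Analysis Plan refers to four groupings without naming them, while the secondary list has eight numbered headings. That 8.9 enters the index is plausible but not stated.
- **Lost power on the primary outcome.** None of the six Vaccine Trust Indicator items is 8.9. Any power figure would need the acceptance rate, the bulletins' effect on the indicator, and whether that effect adds to the ambassador visits. The document gives none of these, and if the effects are additive the dilution is zero.

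**Conclusion.** The point holds for one secondary item, one of nine under its heading, and is minor. Followed as written, the timing and response set leave the endline answer to 8.9 ambiguous for anyone who accepted at baseline, and either simple coding attenuates the between-arm difference. The raw difference shrinks in proportion to baseline enrolment: on the assumed 20% and 27%, from 7 points to 6.3, 4.9 or 3.5 at 10%, 30% or 50% enrolment. These figures illustrate the mechanism and do not forecast this trial. They rest on equal baseline enrolment by arm and on the service existing everywhere. Where there is no service, or where 8.9 was asked only at endline, the problem does not arise. Study-arranged enrolment should be recorded as a feature of both arms; no size can be put on its effect on the primary outcome.

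**What to change.** Confirm from the questionnaire and field records whether 8.9 was asked at baseline in each country. In the Protocol, mark it as endline-only.

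Household Recruitment and Table A1 report baseline as completed, so that mark may come too late. Where the offer was already made:

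1. At endline, ask first whether the respondent already receives the bulletins, and make the offer only to those who do not.
2. Analyse 8.9 among respondents not enrolled at baseline. Baseline enrolment is fixed before the intervention, so the arms stay comparable. Limit this to households where the same person answered both rounds, because the Protocol lets another adult stand in for the head.
3. As a sensitivity analysis, count a respondent as Yes if enrolled at either time.
4. Report baseline sign-ups by arm and country.

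The cost is one filter question and one analysis rule. The downside is fewer respondents in the 8.9 comparison, and a result that applies to those who had not enrolled at baseline, who are probably less receptive than the full sample.
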